Study J1S-MC-JAAA (JAAA; hereinafter referred to as the CAMPFIRE Master Protocol) is a platform to accelerate the development of novel treatments for pediatric and young adult patients with cancer. This platform uses innovative designs and an overarching infrastructure to harness the benefits of shared data and operational efficiencies.

Objectives and Endpoints:

The main purpose of the platform is to create a framework to evaluate the efficacy and safety of Eli Lilly and Company (Lilly) investigational drugs alone or in combination with various available treatments or other investigational agents in specified populations of pediatric and young adult patients as hypotheses emerge. The clinical research objectives and endpoints for specific investigations are detailed in each individual addendum.

Overall Design:

Each investigation consists of the:

1. master document, which defines the platform concept and overall structure, as well as the common elements across all investigations and
2. individual addenda, which define drug/disease-specific hypotheses and investigational requirements.

Each addendum will describe the:

- study population,
- rationale for evaluating the proposed treatment, and
- endpoints and analyses specific to each investigation.

Findings will be reported in addendum-specific study report(s). Once all patients for a particular investigation have met study completion (as defined in that addendum), that addendum will be closed. The master protocol end of study will occur when all addenda have individually completed and no new investigations are planned.

Number of Patients:

Planned enrollment is provided in each specific protocol addendum.

Treatment Arms and Duration:

Administration of the agent(s) being evaluated is described in the specific protocol addendum.

2. Schedule of Activities

This master document defines the platform concept and overall structure, as well as common elements across all investigations. Individual addenda will define study-specific hypotheses and requirements for the study treatment/diseases being evaluated in the investigation. [Table 2.1](#) describes the elements found in the master protocol and addenda.

Table 2.1. Summary of Content of the CAMPFIRE Master Protocol and Protocol Addenda

CAMPFIRE Master Protocol	Addenda

 • Synopsis • Introduction, including the master protocol rationale, and background information about unmet need in pediatric oncology • General inclusion and exclusion criteria • General Discontinuation criteria • Reporting of AEs, SAEs, and SUSARs • General assessment of efficacy, PK, genetics, and biomarkers • Data management methods • Study governance, regulatory requirements, and ethics, including informed consent/assent • List of references cited in the master protocol • List of abbreviations and definitions used in the master protocol 	
 • Investigation-specific synopsis • Background information about the investigation treatment(s) under evaluation, including the rationale for selection of tumor type(s) under investigation, the unmet medical need, and any accompanying investigation treatment(s) • Investigation-specific objectives, endpoints, study design, and statistical plan • Investigation-specific inclusion and exclusion criteria • Study drug administration and dosage modifications for agents under evaluation • Safety lead-in criteria and associated terms (if applicable) • Investigation-specific discontinuation criteria • AEs of special interest • Safety information specific to investigation treatment(s) and/or indication(s) under evaluation (if applicable) • Schedule of activities and schedule for collection of samples for PK, genetics, and biomarker research • Investigation-specific data management methods • List of restricted and prohibited concomitant therapy • List of references cited in the addendum • List of abbreviations and definitions used in the addendum

Abbreviations: AE = adverse event; PK = pharmacokinetics; SAE = serious adverse event; SUSAR = suspected, unexpected serious adverse reaction.

3. Introduction

3.1. Study Rationale

Study J1S-MC-JAAA (JAAA; hereafter referred to as the CAMPFIRE Master Protocol) is a platform to accelerate the development of novel treatments for pediatric and young adult patients with cancer through the use of innovative designs and an overarching infrastructure to harness the benefits of operational efficiencies and shared data. It is designed to be a framework that enables the seamless evaluation of efficacy and safety of Eli Lilly and Company (Lilly) investigational drugs, alone or in combination with various treatments as hypotheses emerge.

3.2. Background

Pediatric cancer drug development can be difficult due to scientific, ethical, and operational challenges. However, there is a critical unmet need for more effective, tolerable, and safe new treatments in order to improve the cure rate, diminish the acute toxic effects associated with existing treatments, and minimize the long-term risks for survivors (Vassal et al. 2013).

A master protocol is an overarching platform that enables concurrent investigation of unique study drug(s) in indication-specific mechanism-of-action driven hypotheses with distinct endpoints through individual addenda, while standardizing structure and operational components under one master construct. This standardization helps facilitate review, ease the burdens of site participation and study execution, speed access, and optimize resources through elimination of redundancy. The flexibility of the standard overarching structure with individual addenda allows for rapid implementation or closing of individual addenda without jeopardizing the other ongoing addenda being investigated. Furthermore, by utilizing innovative designs and adaptive analytics, there is an opportunity to maximize learnings via integration of relevant evidence in specified related addenda. This allows enrollment of a reduced number of patients, while randomizing a greater portion of patients to a novel treatment by conserving control arms and historical data.

Further advantages of using master protocols include, but are not limited to:

- a central governance/review structure to streamline oversight and ensure safety and consistency across the entire platform,
- standardized systems and processes for operational efficiencies and to speed implementation,
- the potential standardization of study template/language across addenda and informed consent forms (ICFs) to ensure consistency and familiarity for ease of review and execution, and for improved compliance,
- a streamlined enrollment procedure that uses the same sites for patient enrollment for increased screening success rates and enhanced study participation,
- a centralized database and informatics infrastructure to facilitate data collection and sharing, enable dynamic decision making, and support additional research,
- the use of Bayesian decision rules and adaptive techniques for randomization and/or analysis,

- the ability to leverage a common control arm across investigations for a specific disease, and the capacity to update the control over time as standards of care evolve,
- the flexibility to add or remove investigations based on early evidence of efficacy and safety, and
- the faster and more reliable acquisition of early-stage data for informing pivotal/confirmatory studies.

Given the high unmet medical need for children and young adults with cancer, Lilly anticipates that a master protocol will provide a more efficient model for assessment of efficacy and safety of novel therapies, whether monotherapy or in combination, for pediatric and young adult patients with cancer. In addition, working with a consistent set of sites across investigations and over time allows for acquired experience to help ensure the safety of patients and improve the quality of study data collected. Together, these attributes of a pediatric master protocol are anticipated to advance research, help speed decision making and accelerate development of the most promising agents and combinations.

3.3. Benefit/Risk Assessment

The direct benefit and risk of experimental treatment regimens are inherent to the compounds making up those regimens. As a result, this component of the benefit risk profile will be particular to each investigation and will be described in the addendum covering it.

Elements of benefit and risk to individual patients that are exclusive to the Master Protocol itself are limited to design and operational aspects of a platform trial. By using shared control cohorts where possible and appropriately incorporating additional information across cohorts, platform trials reduce the number of patients needed to have adequate power to perform multiple investigations and potentially decreases the duration of the investigations. In particular, the number of patients exposed to control arms of potentially less effective therapies is reduced.

On the other hand, the platform trial can introduce complexity for investigators and create the risk of reduced adherence to protocol procedures if consistency between investigations is not maintained. Common schedules of activities, safety assessments and inclusion/exclusion criteria across investigations are specified in the Master Protocol to minimize this risk along with training and appropriate safety monitoring for each investigation.

In conclusion, by providing a clinical trial design that maximizes the available information across multiple investigations and by outlining consistent patient specifications and trial elements across these investigations, this platform trial has a positive benefit risk assessment.

More information about the known and expected benefits, risks, serious adverse events (SAEs), and reasonably anticipated adverse events (AEs) of the investigational study drug(s) used in the individual addendum are to be found in their respective Investigator's Brochures (IBs).

More detailed information about the known and expected benefits and risks of the combination agents may be found in the following: Patient Information Leaflet, Patient Package Insert, or Summary of Product Characteristics.

4. Objectives and Endpoints

The main purpose of the CAMPFIRE Master Protocol is to create a framework to seamlessly evaluate the efficacy and safety of each investigational agent or study drug regimen eligible for development in specified populations of pediatric and young adult patients. Refer to each addendum for specific investigation objectives and endpoints.

5. Study Design

5.1. Overall Design

Each investigation consists of:

1. master document, which defines the platform concept and overall structure, as well as the common elements across all investigations,
2. individual addenda, which define drug/disease-specific hypotheses and investigational requirements.

Each addendum will describe the:

- study population,
- rationale for evaluating the proposed treatment, and
- endpoints and analyses specific to each investigation.

Findings will be reported in investigation-specific study report(s). Once all patients for a particular investigation have met study completion (as defined in that addendum), that investigation will be closed and the end of study declared for that specific investigation once all patients are off study for the particular investigation, including the continued-access phase (Section 7.8). An investigation-specific study report will be produced within one year of the end of study declared for that specific investigation. The CAMPFIRE Master Protocol end of study will occur when all addenda have individually been completed and no new investigations are planned.

Investigations of common scientific interest may leverage information across addenda to maximize learning and minimize redundancy. Examples of this include comparator control arms of common interest. When this involves concurrent investigations within the same patient population, patients will be randomized among the treatment arms within corresponding addenda (see Section 7.2).

Statistical analyses relevant to the specific hypothesis will be found in the relevant addendum and the more detailed addendum statistical analysis plans (SAPs). See Sections 7.2 and 10 for more information.

New addenda will be implemented as hypotheses emerge and new agents become available, compelling new investigations. At any given time, multiple investigations may be open. Once all patients for a particular addendum have met the end of study for that addendum, it will be closed and an appropriate clinical study report will be created for the investigation (Section 5.3).

CCI

5.2. Number of Patients

Planned enrollment will be limited to those needed for the addendum-specified analysis and is provided in Section 3.5.2 of each addendum.

5.3. End of Study Definition

The CAMPFIRE Master Protocol will reach the end of study when all addenda have individually completed and no new addenda are planned.

The end of the study for each investigation is the date of the last visit or last scheduled procedure shown in the Schedule of Activities (Section 3.2 in each addendum) for the last patient.

Refer to Section 3.5.3 in each addendum for the investigation-specific end of study definition.

5.4. Scientific Rationale for Study Design

The scientific rationale regarding the investigation-specific study design is provided in each protocol addendum.

5.5. Justification for Dose

Refer to each investigation-specific addendum for information about the dose(s) selected for each study arm in that addendum.

6. Study Population

Prospective approval of protocol deviations to recruitment and enrollment criteria, also known as protocol waivers or exemptions, is not permitted.

6.1. Inclusion Criteria

Patients are eligible to be included in the study only if they meet all of the following criteria of the CAMPFIRE Master Protocol and the additional criteria for enrollment provided in the protocol addendum to which they are enrolling. Any investigation-specific exceptions to the following criteria in a specific investigation will be described in that addendum; Sections 3.5.1.1 and 3.5.2.1.

- [1] have either measurable or evaluable disease using standard techniques by the Response Evaluation Criteria in Solid Tumors, Version 1.1 (RECIST 1.1) (Eisenhauer et al. 2009).
- [2] The patient, or patient's parent/guardian, has given written informed consent (and assent, as applicable) and authorization for release of health/information for research prior to any study-specific procedures being performed (refer to [Appendix 2](#), Study Governance, Regulatory, and Ethical Considerations).
- [3] The patient has a Lansky (<16 years of age; Lansky et al. 1987) or Karnofsky (\geq 16 years of age; Karnofsky et al. 1948) performance score of at least 50.
- [4] Patients must have discontinued all previous treatments for cancer or investigational agents \geq 7 days after the last dose or as shown below, and must have recovered from the acute effects to \leq Grade 2 for alopecia and decreased tendon reflex and to \leq Grade 1 for all other effects at the time of enrollment, unless otherwise noted. For agents with known AEs occurring beyond the required wait period outlined in the table, this period must be extended until after the time during which the AE is known to occur. Consult with the Lilly CRS/CRP for the appropriate length of time prior to the first dose of study treatment on additional therapies not mentioned.

Previous Treatment	Length of Time Prior to First Dose of Study Treatment
Cytotoxic and myelosuppressive chemotherapy	\geq 14 days after the last dose of cytotoxic or myelosuppressive chemotherapy (or \geq 42 days if prior nitrosourea)
Hematopoietic growth factors	\geq 14 days after the last dose of a long-acting growth factor (for example, pegfilgrastim) or \geq 48 hours for short-acting growth factor
Cellular therapy	\geq 42 days after the completion of any type of cellular therapy (eg modified T cells, NK cells, dendritic cells, etc.) agent
Interleukins, interferons, and cytokines (other than	\geq 21 days after the completion of interleukins,

Previous Treatment	Length of Time Prior to First Dose of Study Treatment
hematopoietic growth factors)	interferon, or cytokines (other than hematopoietic growth factors)
Antibody therapy	≥21 days after the last infusion of antibody therapy
Radiotherapy	≥ 14 days since local palliative radiation therapy (RT) (small port); craniospinal XRT, or 50% or greater pelvic radiation; ≥ 42 days for other substantial radiation (such as metaiodobenzylguanidine therapy)
Radiopharmaceutical therapy (eg, radiolabeled antibody, 131I-MIBG)	≥42 days after systemically administered radiopharmaceutical therapy
Stem cell infusion without TBI	≥84 days must have elapsed after auto-transplant or stem cell infusion
Corticosteroids	≥14 days for patients who have received a course of systemic corticosteroids (≥5 days) to modify immune AEs related to prior therapy. Note: Patients who are on chronic replacement dose for endocrine disorders or are on a stable or decreasing dose for indications other than treating the underlying cancer, may still be eligible (consult Lilly CRP/CRS)
Live vaccines	≥28 days after last live vaccine

[5] The patient has adequate hematologic and organ function ≤1 week (7 days) prior to first dose of study drug:

System	Laboratory Value
Hematologic	
ANC	$\geq 1000/\mu\text{L}$ G-CSF permitted up to 48 hours prior. Patients with documented history of benign ethnic neutropenia or other conditions could be considered with a lower ANC after discussion with and approval from the Lilly CRP/CRS
Platelets	$\geq 75,000/\text{mm}^3$ Platelet transfusion permitted up to 72 hours prior.
Hemoglobin	$\geq 8 \text{ g/dL}$ ($\geq 80 \text{ g/L}$) Transfusions to increase the patient’s hemoglobin level to at least 8 g/dL are permitted; however, study treatment must not begin until 7 days after the transfusion. and CBC criteria for eligibility are confirmed within 24 hr of C1D1
Hepatic	
Total bilirubin	$\leq 1.5 \times \text{ULN}$ Except patients with document history of Gilbert Syndrome who must have a total bilirubin level of $< 3.0 \times \text{ULN}$
ALT and AST	$\leq 2.5 \times \text{ULN}$ OR $\leq 5.0 \times \text{ULN}$ if the liver has tumor involvement

Abbreviations: ALT = alanine aminotransferase; ANC = absolute neutrophil count; AST = aspartate aminotransferase; CBC = complete blood count; ULN = upper limit of normal.

- Creatinine clearance or radioscope glomerular filtration rate (GFR) $\geq 60 \text{ mL/min/m}^2$ (Appendix 4) OR
- Serum creatinine meeting the following parameters:
 - for patients ≥ 18 years of age serum creatinine $\leq 1.5 \times$ upper limit of normal (ULN);
 - for patients < 18 years of age, serum creatinine based on age/gender as follows:

Age	Maximum Serum Creatinine (mg/dL)	
	Male	Female
1 to < 2 years	0.6	0.6
2 to < 6 years	0.8	0.8
6 to < 10 years	1.0	1.0
10 to < 13 years	1.2	1.2
13 to < 16 years	1.5	1.4
16 to < 18 years	1.7	1.4

The threshold creatinine values in this table were derived from the Schwartz formula for estimating glomerular filtration rate (Appendix 4).

- [6] Female patients of childbearing potential must have a negative urine or serum pregnancy test within 7 days prior to Cycle 1 Day 1.
- [7] Both female and male patients of childbearing potential must agree to use highly effective contraceptive precautions during the trial and for at least 3 months following the last dose of study drug, or longer, if appropriate for other study drugs according to their label in order to prevent pregnancy.

Females of childbearing potential (FOCBP) and males who are abstinent (if this is complete abstinence, as their preferred and usual lifestyle) or in a same-sex relationship (as part of their preferred and usual lifestyle) must agree to either remain abstinent or stay in a same-sex relationship without sexual relationships with someone of the opposite sex. Periodic abstinence (e.g., calendar, ovulation, symptothermal, or postovulation methods), declaration of abstinence just for the duration of a trial, and withdrawal are not acceptable methods of contraception.

Females: FOCBP participating must test negative for pregnancy prior to initiation of treatment as indicated by a negative urine or serum pregnancy test at the screening visit. Two forms of effective contraception, where at least one form is highly effective (less than 1% failure rate; includes combination oral contraceptives, implanted contraceptives, or intrauterine devices) must be used. Effective contraception (such as male or female condoms with spermicide, diaphragms with spermicide, or cervical sponges) may be used as the second therapy. Barrier protection methods without concomitant use of a spermicide are not a reliable or acceptable method. Thus, each barrier method must include use of a spermicide (i.e., condom with spermicide, diaphragm with spermicide, or female condom with spermicide). It should be noted that the use of male and female condoms as a double barrier method is not considered acceptable due to the high failure rate when these methods are combined.

Males: Males, regardless of their fertility status, with nonpregnant FOCBP partners must agree to use condoms as well as one additional highly effective method of contraception (less than 1% failure rate; includes combination oral contraceptives, implanted contraceptives, or intrauterine devices) for the duration of the study and up to 3 months following the last dose of study drug, or longer, if appropriate for other study drugs according to their label in order to prevent pregnancy.

Barrier protection methods without concomitant use of a spermicide are not an effective or acceptable method of contraception. Thus, each barrier method must include use of a spermicide. It should be noted, however, that the use of male and female condoms as a double barrier method is not considered acceptable due to the high failure rate when these barrier methods are combined. Males with pregnant partners should use condoms during intercourse for the duration of the study and for at least 3 months after the last

dose of study drug, or longer, if appropriate for any study drug according to the label.

- [34] Pediatric and young adult patients will be enrolled, where the specific age requirement for each indication will be specified in the protocol addenda

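### The radiotherapy washout row gives craniospinal and large-field pelvic radiation no interval of their own, so as written they need 14 days while other substantial radiation needs 42

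*Protocol*

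**What the plan says.** Criterion [4] in Protocol Section 6.1 requires prior cancer treatment to have stopped at least 7 days earlier, or for the period shown in a table by type of treatment. The radiotherapy row starts at 14 days or more and reads on "since local palliative radiation therapy (RT) (small port); craniospinal XRT, or 50% or greater pelvic radiation; ≥ 42 days for other substantial radiation". The 42-day part carries an example: "≥ 42 days for other substantial radiation (such as metaiodobenzylguanidine therapy)". The next row, for radiopharmaceuticals, asks for "≥42 days after systemically administered radiopharmaceutical therapy".

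Three general provisions surround the table:

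- **Recovery.** Acute effects must have resolved to "Grade 1 for all other effects at the time of enrollment", with Grade 2 allowed for alopecia and decreased tendon reflex.
- **Extension.** "For agents with known AEs occurring beyond the required wait period outlined in the table, this period must be extended" until the period of that risk has passed.
- **Consultation.** The sponsor's clinical research physician or scientist is to be asked about the interval "prior to the first dose of study treatment on additional therapies not mentioned".

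An addendum may state exceptions to the master criteria. Section 6 rules out waivers of enrolment criteria.

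**The concern.** The row names the large fields but attaches no number of days to them. The only interval before them is 14 days, so a site reading from left to right will apply 14 days. On that reading, craniospinal or extensive pelvic irradiation is treated like a small palliative port, and is held to a shorter washout than substantial radiation the row does not name.

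Two things are at stake. The first is safety: the likelier literal reading is the less protective one. The second is consistency. Section 3.3 relies on shared eligibility criteria in the master protocol to keep investigations aligned, and Section 7.8.1 foresees up to about 10 of them. Section 8.1.1 requires enrolment criteria to be followed explicitly, which cannot be done when a criterion supports two answers. A patient enrolled at one site on the 14-day reading could be judged inadvertently enrolled by someone using the 42-day reading.

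**Working it through.** No sample-size, power or error-rate figure is involved. The check is a clause-by-clause reading of the row, followed by simple differences.

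**The row, split at its semicolons (Section 6.1 [4])**

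| Segment | Radiation | Interval stated |
|---|---|---|
| 1 | Local palliative, small port | 14 days or more |
| 2 | Craniospinal, or at least half the pelvis | none |
| 3 | Other substantial radiation | 42 days or more |

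**Possible readings of segment 2**

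- *Carried over from segment 1:* 14 days. This is the natural reading in sequence, but it clashes with 'other' in segment 3, which implies that the fields just named are substantial too.
- *Grouped with segment 3:* 42 days. This agrees with 'other', but the 42 days is attached only to what follows the second semicolon.
- *No interval in the table:* the general 7 days in the lead-in to [4]. This is the least likely reading, though the missing number does not exclude it.

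**Size of the discrepancy between the two main readings**

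- Difference: 42 − 14 = 28 days.
- Ratio: 42 / 14 = 3.
- Days on which they give opposite answers: day 14 to day 41 inclusive, 41 − 14 + 1 = 28 days.

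**Does other text settle it?**

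- The consultation clause covers therapies that are not mentioned. These fields are mentioned.
- The extension clause speaks of agents with known later adverse events. Even if radiation counts as an agent, the clause gives no number.
- Criterion [5] sets blood-count limits but no time since radiation. The neutrophil limit may be met with G-CSF up to 48 hours before, and the platelet limit with transfusion up to 72 hours before. Only the haemoglobin entry imposes a wait, 7 days after a transfusion.
- No other section gives a craniospinal or pelvic interval.

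**Comparison within the table.** Forty-two days appears in four entries: "42 days if prior nitrosourea", "42 days after the completion of any type of cellular therapy", other substantial radiation, and radiopharmaceutical therapy. The last two overlap, since both cite MIBG treatment, and the first two say nothing about external radiation. The count shows that 42 days is a familiar interval in this table. It does not show that 42 days was meant for these fields.

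**The case against.** The strongest reply is that the row is complete as it stands: 14 days governs all three fields listed before the second semicolon, and 42 days governs the rest. The only example of the 42-day class is MIBG therapy, a systemic treatment, so 'other' may simply separate that class from the external-beam fields before it. On this view the complaint becomes a clinical opinion that 14 days is too short, and the protocol holds no toxicity or marrow-recovery data to support that.

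Part of this stands. The protocol does not show what was intended, and the harm of a 14-day wait cannot be measured from it. But the reply does not make the row coherent. It still calls unnamed radiation 'other substantial' directly after naming the large fields, and gives those fields the small-port interval.

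The safeguards also count for something. Recovery to Grade 1 applies whatever the interval. Blood counts are to be confirmed within 24 hours of Cycle 1 Day 1. A separate table row requires 14 days after long-acting and 48 hours after short-acting growth factors. If radiation is taken to be an agent, the extension clause is mandatory. These limit the practical harm, but none sets a minimum time since radiation.

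Finally, each investigation has its own addendum, reviewed as an independent application, and may state an exception. Where an addendum is silent, however, the master row is the rule.

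**Conclusion.** The concern holds. The row names three categories of radiation and gives two intervals. Followed as written, it can admit a patient 14 to 41 days after craniospinal or large pelvic irradiation, while a patient given other substantial radiation must wait 42 days: a 28-day, threefold difference.

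That the interval is missing is plain from the text. That 42 days is the right minimum is an inference from the word 'other', and needs the sponsor's confirmation. How many patients are affected, and how much excess toxicity might follow, cannot be derived from the protocol. No endpoint, sample size or analysis is touched. The row should be corrected because it is a binding eligibility rule that bears on safety and applies by default across the platform.

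**What to change.** Give the large fields their own interval. Suggested wording for the row: at least 14 days since small-port local palliative radiotherapy; at least 42 days since craniospinal radiotherapy, radiation to half or more of the pelvis, or any other substantial radiation.

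The 42 days is a floor taken from the row's own substantial class. The sponsor should confirm the intended figure, and the clinical team may prefer a longer one. If 14 days was deliberate, the row should say so for these fields and drop the implication that they belong with the 42-day class. Open addenda should be checked for an exception that already fixes the interval.

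The cost is one table row in the next amendment. Relative to the 14-day reading, the added wait for an interval of X days is X − 14. At 42 days, a few patients may wait up to 28 days longer. At 84 days, the longest interval in the table (from the stem-cell row, shown only as the end of the range), it would be 84 − 14 = 70 days.
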